10.4.2.2. ICANS Incidence

Incidence of ICANS, defined as the percentage of participants experiencing ICANS over 28-day period, will be presented together with its exact 95% CI. In addition, the most severe ICANS within each participant will be summarized by frequency count. There is no missing data imputation in calculation of ICE score or ICANS grading. In addition, ICANS incidence will be provided separately for each IEC therapy.

10.4.2.3. Onset and Duration of ICANS

Time to first onset of ICANS from date of IEC infusion will be summarized within the first 28 days. Participants without ICANS will be considered as missing and not included in the summary. Duration of multiple occurrence of ICANS within each participant will be added together regardless of grading. Summary statistics including mean, median, standard deviation, minimum, and maximum will be provided for time to first onset of ICANS and duration of ICANS.

10.4.2.4. Onset and Duration of CRS

Time to first onset of CRS from date of IEC infusion will be summarized within the first 28 days. Participants without CRS will be considered as missing in the summary statistics. Duration of multiple occurrence of CRS within each participant will be added together regardless of grading. Summary statistics including mean, median, standard deviation, minimum, and maximum will be provided for time to first onset of CRS and duration of CRS.

10.4.2.5. Occurrence of CRS Within 48 Hours

Percentage of participants who developed CRS within 48 hours of IEC infusion will be summarized. Two-sided 95% exact CI will be provided.

10.4.2.6. CRS Rate Within 28 Days

Percentage of participants who developed CRS within 28 days of IEC infusion will be summarized. Two-sided 95% exact CI will be provided.

10.4.2.7. Hospitalization on Study

Number of hospitalization associated with total duration of hospitalization will be summarized. Cause of hospitalization will be provided as well.

10.4.3. Safety Analyses

Safety analyses will be conducted for the safety population. All safety will be summarized by IEC therapy and overall population. Specific safety may also be summarized by underlying disease as needed.

Safety summaries will also be presented by the 2 dose groups and placebo for all the safety endpoints that are described below. This additional information will be used to confirm the optimal dose selection.

10.4.3.1. Adverse Events

Adverse events will be coded by the Medical Dictionary for Regulatory Activities dictionary, and TEAEs (ie, AEs reported for the first time or worsening of a pre-existing event after first dose of study treatment) will be tabulated by preferred term and system organ class for all events, related events, and events of Grade 3 or higher.

10.4.3.2. Clinical Laboratory Tests

The clinical laboratory data will be analyzed using summary statistics. In addition, distributions of key laboratory parameters may be plotted over time; these values will also be classified into CTCAE toxicity grades and tabulated.

Laboratory test values outside the normal range will be assessed for severity based on the normal ranges for the clinical reference laboratory. The incidence of abnormal laboratory values and shift tables relative to baseline will be tabulated. The following summaries will be produced for the laboratory data:

[figure not shown]
- Number and percentage of participants with worst post baseline CTCAE grade (regardless of baseline value). Each participant will be counted only for the worst grade observed postbaseline.
- Shift tables from baseline to the worst post baseline value using CTCAE grade.
- For laboratory parameters where CTCAE grades are not defined, shift tables to the worst post baseline value using the low/normal/high classifications based on laboratory reference ranges.

10.4.3.3. Vital Signs

Descriptive statistics and mean change from baseline will be determined for vital signs (blood pressure, pulse, respiratory rate, and body temperature) at each assessment time. Vital sign results will be reviewed for clinically notable abnormalities, and participants exhibiting clinically notable vital sign abnormalities will be listed.

10.4.3.4. Dose Intensity

Measures of exposure (eg, days of exposure, drug compliance, dose intensity) of study drug will be summarized by means of summary statistics.

10.5. Interim Analysis

For Part 1, an interim analysis is planned after approximately 24 participants are dosed with IEC therapy and complete the Day 28 (EOT) visit. The results from the interim analysis will be reviewed by the DSMB. The primary intent of this analysis is to minimize unnecessary exposure to itacitinib in the event of futility of preventing CRS. The study may be stopped for futility at the interim analysis if the conditional power based on interim results is lower than 20%, which is

equivalent to more than 17 out of 24 participants experiencing \geq Grade 2 CRS by Day 14. More than 24 participants may be available in EAS at the time of interim analysis, and the stopping boundary will be re-evaluated at the time of the analysis. [REDACTED]

[REDACTED] Enrollment will continue while the analysis is being conducted, and the study Statistical Analysis Plan will describe the planned interim analysis in greater detail.

No interim analysis is planned for Part 2.

11. SUPPORTING DOCUMENTATION AND OPERATIONAL CONSIDERATIONS

11.1. Investigator Responsibilities

- The Protocol, Protocol Amendments, ICF, IB, and other relevant documents (eg, advertisements) must be submitted to an IRB/IEC by the investigator and reviewed and approved by the IRB/IEC and health authorities before the study is initiated.
- The investigator is responsible for ensuring that the safety reports provided by the sponsor are reviewed and processed in accordance with regulatory requirements, the policies and procedures established by the IRB/IEC, and institutional requirements.
- Any amendments to the Protocol will require approval from both health authorities and the IRB/IEC before implementation of changes made to the study design, except for changes necessary to eliminate an immediate hazard to study participants.
- The investigator will be responsible for the following:
 - Providing written summaries of the status of the study to the IRB/IEC annually or more frequently in accordance with the requirements, policies, and procedures established by the IRB/IEC.
 - Notifying the IRB/IEC of SAEs or other significant safety findings as required by IRB/IEC procedures.
 - Providing oversight of the conduct of the study at the site and adherence to GCP, IRB/IEC requirements, institutional requirements, and applicable laws and country-specific regulations.
- Adhering to the Protocol as described in this document and agreeing that changes to the Protocol procedures, with the exception of medical emergencies, must be discussed and approved, first, by the sponsor or its designee and, second, by the IRB/IEC. Each investigator is responsible for enrolling participants who have met the specified eligibility criteria.
- Retaining records in accordance with all local, national, and regulatory laws but for a minimum period of at least 2 years after the last marketing application approval in an ICH region and until there are no pending or contemplated marketing applications in an ICH region, or if not approved, 2 years after the termination of the test article for investigation to ensure the availability of study documentation should it become necessary for the sponsor or a regulatory authority to review.
 - The investigator must not destroy any records associated with the study during the retention period without receiving approval from the sponsor. The investigator must notify the sponsor or its designee in the event of accidental loss or destruction of any study records. If the investigator leaves the institution where the study was conducted, the sponsor or its designee must be contacted to arrange alternative record storage options.

- All eCRF data entered by the site (including audit trail), as well as computer hardware and software (for accessing the data), will be maintained or made available at the site in compliance with applicable record retention regulations. The sponsor will retain the original eCRF data and audit trail.

11.2. Data Management

Data management will be performed in a validated EDC system. The investigator will be provided with access to an EDC system so that an eCRF can be completed for each participant.

The site will be provided with eCRF completion guidelines for instructions on data entry in the eCRF. The study monitor will reference the Monitoring Plan in order to ensure that each issue identified is appropriately documented, reported, and resolved in a timely manner in accordance with the plan's requirements. Other data outside the EDC system required in the study conduct of the Protocol, such as documents or results transmitted to the sponsor via a central laboratory or specialized technical vendors, and as designated by the sponsor, will have their own data flow management plans, or study charters, or [REDACTED] plans, as applicable.

The sponsor (or designee) will be responsible for the following:

- Managing the integrity of the data and the quality of the conduct of the study, such as ensuring that study monitors perform ongoing source data verification to confirm that data entered into the eCRF by authorized site personnel are accurate, complete, and verifiable from source documents; that the safety and rights of participants are being protected; and that the study is being conducted in accordance with the currently approved Protocol and any other study agreements, ICH GCP, and all applicable regulatory requirements.
- Managing and reconciling the data generated and/or collected, including documents and results such as laboratory or imaging data analyzed centrally by a designated vendor of the sponsor.

The investigator will be responsible for the following:

- Recording, or ensuring the recording of, all relevant data relating to the study in the eCRF.
- Delivering, or ensuring the delivery of, all other results, documents, data, know-how, or formulas relating to the study to the sponsor or designee electronically and/or centrally (eg, laboratory data, imaging data, [REDACTED] photographs, diary data) or as otherwise specified in the Protocol.
- Maintaining adequate and accurate source documents and trial records that include all pertinent observations on each of the site's trial participants. Source data should be attributable, legible, contemporaneous, original, accurate, and complete. Changes to source data should be traceable, should not obscure the original entry, and should be explained if necessary (eg, via an audit trail). Source data are, in general, all information in original records and certified copies of original records of clinical findings, observations, or other activities in a clinical trial necessary for the reconstruction and evaluation of the trial. Source data are contained in source documents (original records or certified copies).

- Verifying that data entries are accurate and correct by physically or electronically signing the eCRF.
- Maintaining accurate documentation (source data) that supports the information entered in the eCRF, sent to a central vendor designated by the sponsor, or as described in other study and data flow manuals.
 - Source documents provide evidence for the existence of the participant and substantiate the integrity of the data collected. Source documents are filed and available at the investigator's site. Examples of source documents are original documents, data, and records (eg, hospital records; electronic hospital records; clinical and office charts; laboratory notes; memoranda; participants' diaries or evaluation checklists; pharmacy dispensing records; recorded data from automated instruments; copies or transcriptions certified after verification as being accurate copies; microfiches; photographic negatives; microfilm or magnetic media; x-rays; participants' files; and e-records/records kept at the pharmacy, at the laboratories, and at medico-technical departments involved in the clinical trial).
 - Data entered in the eCRF that are transcribed from source documents must be consistent with the source documents or the discrepancies must be explained. The investigator may need to request previous medical records or transfer records, depending on the study. Current applicable medical records must be available.
- Sending participants' data, either as unique samples, copies, or photographs, to be evaluated centrally or analyzed centrally, or both, by a qualified vendor designated by the sponsor.
 - As required by privacy and data protection regulations and Incyte's privacy policies, if any photographs of participants are to be taken, the photographs must be limited to the area of the face or the body that is strictly necessary and the photographs should be masked (ie, identifying features such as eyes, mouth, scars, tattoos, or unique markings or features should be either obscured with a black bar or digitally pixelated so as to not permit the reidentification of the participants and preserve their confidentiality) by a specially designated photography vendor prior to sending the photographs to Incyte or any other third-party vendors for analysis or further processing.
- Permitting study-related monitoring, sponsor audits, IRB/IEC review, and regulatory inspections by providing direct access to source data and other relevant clinical study documents.
 - Monitoring: Qualified representatives of the sponsor or its designee, study monitors, will monitor the study according to a predetermined plan. The investigator must allow the study monitors to review any study materials and participant records at each monitoring visit.

- Auditing: Qualified representatives of the sponsor or its designee may audit the clinical study site and study data to evaluate compliance with the Protocol, applicable local clinical study regulations, and overall study conduct. The investigator must allow the auditors to review original source records and study documentation for all participants.
- Regulatory inspection: Regulatory authorities may conduct an inspection of the study and the site at any time during the development of an investigational product. The investigator and staff are expected to cooperate with the inspectors and allow access to all source documents supporting the eCRFs and other study-related documents. The investigator must immediately notify the sponsor when contacted by any regulatory authority for the purposes of conducting an inspection.

11.3. Data Quality Assurance

The sponsor assumes accountability for actions delegated to other individuals (eg, contract research organizations). The sponsor or designee is responsible for the data management of this study, including quality checking of the data. Further, monitoring details describing strategy, including definition of study-critical data items and processes (eg, risk-based initiatives in operations and quality such as risk management and mitigation strategies and analytical risk-based monitoring), methods, responsibilities, and requirements, including handling of noncompliance issues, Protocol deviations, and monitoring techniques (eg, central, remote, or on-site monitoring) are provided in the monitoring plan.

Quality tolerance limits will be predefined in the operational manual to identify systematic issues that can impact participants' safety, efficacy results and analysis, and/or reliability of study results. These predefined parameters will be monitored during the study and can be adjusted during the study upon data review. Important deviations from the quality tolerance limits and remedial actions taken, including reporting to IRBs/IECs and health authorities if applicable, will be summarized in the CSR.

11.4. Data Privacy and Confidentiality of Study Records

The investigator and the sponsor or its designee must adhere to applicable data protection laws and regulations. The investigator and the sponsor or its designee are responsible for ensuring that personal information is handled in accordance with local data protection laws (including, but not limited to Health Insurance Portability and Accountability Act of 1996 and General Data Protection Regulation) as applicable, and the sponsor operates comprehensive data privacy and data security programs that are applicable to this study. Appropriate notice, or notice and consent (as may be required by each applicable jurisdiction), for collection, use, disclosure, and/or transfer (if applicable) of personal information must be obtained in accordance with local data protection laws. Appropriate data protection terms that comply with applicable laws will be included in relevant study agreements.

To ensure confidentiality of records and protect personal data, participant names will not be supplied to the sponsor or its designee. Only the participant number will be recorded in the eCRF; if the participant's name appears on any other document (eg, laboratory report), it must be obliterated on the copy of the document to be supplied to the sponsor or its designee. Study

findings stored on a computer will be stored in accordance with appropriate technical and organizational measures as required by local data protection laws.

In the event of a data breach involving participant data, the sponsor or its designee will follow the sponsor's incident response procedures. The precise definition of a data breach varies in accordance with applicable law but may generally be understood as a breach of security leading to the accidental or unlawful destruction, loss, alteration, unauthorized disclosure of, or access to, personal data. In accordance with its incident response procedures, the sponsor will assess the breach to consider its notification and remediation obligations under applicable law.

11.5. Financial Disclosure

Before study initiation, all clinical investigators participating in clinical studies subject to FDA Regulation Title 21 CFR Part 54 – Financial Disclosure by Clinical Investigators (ie, "covered studies") are required to submit a completed Clinical Investigator Financial Disclosure form that sufficiently details any financial interests and arrangements that apply. For the purpose of this regulation, "clinical investigator" is defined as any investigator or subinvestigator who is directly involved in the treatment or evaluation of research participants, including the spouse and each dependent child of the clinical investigator or subinvestigator. These requirements apply to both US and foreign clinical investigators conducting covered clinical studies.

Any new clinical investigators added to the covered clinical study during its conduct must also submit a completed Investigator Financial Disclosure Form. During a covered clinical study, any changes to the financial information previously reported by a clinical investigator must be reported to the sponsor or its designee. At the conclusion of the covered clinical study, the clinical investigators will be reminded of their obligations. In the event that the clinical investigator is not reminded, they nevertheless will remain obligated to report to the sponsor or its designee any changes to the financial information previously reported, as well as any changes in their financial information for a period of 1 year after completion of the covered clinical study.

11.6. Publication Policy

By signing the study Protocol, the investigator and their institution agree that the results of the study may be used by the sponsor, Incyte Corporation (Incyte), for the purposes of national and international registration, publication, and information for medical and pharmaceutical professionals. Study results will be published in accordance with applicable local and national regulations. If necessary, the authorities will be notified of the investigator's name, address, qualifications, and extent of involvement. The terms regarding the publication of study results are contained in the agreement signed with the sponsor or its designee. A signed agreement will be retained by the sponsor or its designee.

The results of this study may be published or presented at scientific meetings. If this is foreseen, the investigator agrees to submit all manuscripts or abstracts to the sponsor before submission. This allows the sponsor to protect proprietary information and to provide comments.

The sponsor will comply with the requirements for publication of study results. In accordance with standard editorial and ethical practice, the sponsor will generally support publication of multicenter studies only in their entirety and not as individual site data. In this case, a coordinating investigator will be designated by mutual agreement.

Authorship will be determined in line with International Committee of Medical Journal Editors authorship requirements.

11.7. Study and Site Closure

The sponsor designee reserves the right to close the study site or terminate the study at any time for any reason at the sole discretion of the sponsor. Study sites will be closed upon study completion. A study site is considered closed when all required documents and study supplies have been collected and a study-site closure visit has been performed.

The investigator may initiate study-site closure at any time, provided there is reasonable cause and sufficient notice is given in advance of the intended termination.

Reasons for the early closure of a study site by the sponsor or investigator may include but are not limited to:

- Failure of the investigator to comply with the protocol, the requirements of the IRB or local health authorities, the sponsor's procedures, or GCP guidelines.
- Inadequate recruitment of participants by the investigator.
- Discontinuation of further study treatment development.

APPENDIX A. INFORMATION REGARDING EFFECTIVENESS OF CONTRACEPTIVE METHODS

For male participants in the study:

Male participants should use a condom from screening through 90 days after the end of systemic exposure. If the male participant has a partner that is of child-bearing potential, the partner should also use contraception through 90 days after the end of relevant systemic exposure. In addition, male participants must refrain from donating sperm from screening through 90 days after the end of relevant systemic exposure. Males who have had a vasectomy qualify as having met the requirement for a highly effective birth control method.

For female participants in the study:

The following methods that can achieve a failure rate of less than 1% per year when used consistently and correctly are considered as highly effective birth control methods:

- Combined (estrogen and progestogen containing) hormonal contraception associated with inhibition of ovulation^a
 - oral
 - intravaginal
 - transdermal
- Progestogen-only hormonal contraception associated with inhibition of ovulation^a
 - oral
 - injectable
 - implantable^b
- Intrauterine device^b
- Intrauterine hormone-releasing system^b
- Bilateral tubal occlusion^b
- Vasectomized partner^{bc}
- Sexual abstinence^d

Acceptable birth control methods that result in a failure rate of more than 1% per year include:

- Progestogen-only oral hormonal contraception, where inhibition of ovulation is not the primary mode of action
- Male or female condom with or without spermicide^e
- Cap, diaphragm, or sponge with spermicide^e
- Tubal ligation

^a Hormonal contraception may be susceptible to interaction with the investigational medicinal product, which may reduce the efficacy of the contraception method.

^b Contraception methods that in the context of this guidance are considered to have low user dependency.

^c Vasectomized partner is a highly effective method of avoiding pregnancy provided that partner is the sole sexual partner of the woman of childbearing potential study participant and that the vasectomized partner has received medical assessment of the surgical success.

^d In the context of this guidance, sexual abstinence is considered a highly effective method only if defined as refraining from heterosexual intercourse during the entire period of risk associated with the study treatments. The reliability of sexual abstinence needs to be evaluated in relation to the duration of the clinical study and the preferred and usual lifestyle of the participant.

^e A combination of male condom with either cap, diaphragm, or sponge with spermicide (double barrier methods) are also considered acceptable, but not highly effective, birth control methods.

Source: [Clinical Trial Facilitation Group 2014](#).

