In Part 2, study treatment is defined as itacitinib 200 mg BID or placebo beginning at Day -3 (pre-IEC) through Day 26 (post-IEC), counting for a total of 30 days of treatment.

See [Figure 1](#) for the study design and [Table 3](#) for the SoA. Adherence to the study design requirements, including those specified in the SoA, is essential and required for study conduct.

Figure 1: Study Design Schema Part 1

Part 1

[figure not shown]

Figure 2: Study Design Schema Part 2

Part 2

[figure not shown]

Table 3: Schedule of Activities

	Screening ^a		Study Treatment								Post-Treatment Follow-Up ^a			Protocol Section
	D -17 to D -4	D -3	D -1	IEC D0	D1	D3	D5	D7	D14 (± 2 d)	D21 (± 2 d)	EOT ^b D28 (± 2 d)	D56 30 d After Last Dose (± 3 d)	D90 (± 1 wk)	EOS D180 (± 2 wk)
Administrative procedures														
Informed consent	X													8.1.1
Contact IRT	X	X									X			8.1.3
Inclusion/exclusion criteria	X	X	X											5.1, 5.2
Demography/medical history	X													8.1.5
Prior/concomitant medications	X	X	X	X	X	X	X	X	X	X	X			6.3
Administer study treatment		X	X	X	X	X	X	X	X	X				6.1
Administer IEC therapy			X											6.2
Document compliance		X	X	X	X	X	X	X	X	X	X			6.1.2
Dispense reminder cards	X	X	X	X	X	X	X	X	X	X	X	X	X	8.1.4
Drug accountability		X	X	X	X	X	X	X	X	X	X			6.1.1
Survival follow-up												X	X	8.9.4
Safety assessments														
Adverse events	X	X	X	X	X	X	X	X	X	X	X	X		8.3.1
ECOG	X		X						X		X			8.3.4
Physical examination	X		X								X			8.3.2
Vital signs	X	X	X	X	X	X	X	X	X	X	X	X		8.3.3
ECHO	X													8.9.3
12-lead ECG	X													8.9.3
Disease assessments														
FDG-PET CT/MRI ^c	X										X		X	8.4
Bone marrow evaluation	X													8.4
Endpoint assessments														
Temperature monitoring		X	X	X	X	X	X	X	X	X	X			8.3.3
CRS assessment (ASBMT CRS consensus grading) ^d											X			8.2.1
ICANS assessment (ASBMT ICE consensus grading) ^e											X			8.2.2
Lee's CRS revised grading system			X	X	X	X	X	X	X	X	X	X	X	8.2.3

Table 3: Schedule of Activities (Continued)

	Screening ^a	Study Treatment										Post-Treatment Follow-Up ^a			Protocol Section
		D -17 to D -4	D -3	D -1	IEC D0	D1	D3	D5	D7	D14 (± 2 d)	D21 (± 2 d)	EOT ^b D28 (± 2 d)	D56 30 d After Last Dose (± 3 d)	D90 (± 1 wk)	EOS D180 (± 2 wk)
Local laboratory assessments^f															
Hematology	X	X		X	X	X	X	X	X	X	X	X	X	8.3.5	
Serum chemistries (including LDH)	X	X		X	X	X	X	X	X	X	X			8.3.5	
Coagulation panel	X	X				X					X			8.3.5	
Lipid panel	X										X			8.3.5	

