5.1. Inclusion Criteria

Participants are eligible to be included in the study only if all of the following criteria apply:

1. Part 1: Male or female, 12 years of age or older. The participant (or legally acceptable representative for participants < 18 years of age) has the ability to comprehend and provides written informed consent for the study.

Note: The participants who are < 18 years of age will have a parent or legal guardian able to give written informed consent and assent (as appropriate) according to institutional standards and to comply with all study visits and procedures.

Part 2: Male or female, 18 years of age or older.

2. Eligible to receive an IEC therapy that is approved by the health authority in the country where the study is being conducted, for hematologic indications.

Part 1: Eligible to receive any IEC therapy for any approved indication.

Part 2: Eligible to receive Yescarta for relapsed or refractory large B-cell lymphoma or follicular lymphoma.

3. ECOG performance status 0 to 1.

4. Willingness to avoid pregnancy or fathering children based on the criteria below.

- a. Men must agree to take appropriate precautions to avoid fathering children (with at least 99% certainty) from screening through safety follow-up and must refrain from donating sperm during this period. Permitted methods that are at least 99% effective in preventing pregnancy (see [Appendix A](#)) should be communicated to the participants and their understanding confirmed.
- b. Women of childbearing potential must have a negative serum pregnancy test at screening and before the first dose on Day 1 and must agree to take appropriate precautions to avoid pregnancy (with at least 99% certainty) from screening through safety follow-up. Permitted methods that are at least 99% effective in preventing pregnancy (see [Appendix A](#)) should be communicated to the participants and their understanding confirmed.
- c. Women of nonchildbearing potential (ie, surgically sterile with a hysterectomy and/or bilateral oophorectomy OR ≥ 12 months of amenorrhea) are eligible.

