7.1.2. Discontinuation Procedures

In the event that the decision is made to permanently discontinue the study treatment before Day 28, the EOT visit should be conducted. Reasonable efforts should be made to have the participant return for a 30-day safety follow-up visit. These visits are described in [Table 3](#). The last date of the last dose of itacitinib and the reason for discontinuation of study treatment will be recorded in the eCRF.

If a participant is discontinued from study treatment:

- The study monitor or sponsor must be notified.
- The reason(s) for withdrawal must be documented in the participant's medical record and the primary reason for withdrawal must be included in the eCRF.
- The EOT visit should be performed.
- The date of the EOT visit should be recorded in the IRT.
- Participants must be followed for safety until the time of the 30-day follow-up visit or until itacitinib-related toxicities resolve, return to baseline, or are deemed irreversible, whichever is longest.

If the participant discontinues study treatment and actively withdraws consent for collection of follow-up data (safety follow-up or survival follow-up), then no additional data collection should occur; however, participants will have the option of withdrawing consent for study treatment but continuing in the follow-up period of the study.

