8.8. End of Treatment

Per the Protocol, Day 26 is the last expected day of study treatment administration. An EOT visit will be conducted at Day 28 (\pm 2 days).

If the participant discontinues study treatment before Day 26, the EOT visit will still be conducted.

Unless the participant withdraws consent, all study assessments should continue to be performed and captured in the eCRF.

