8.9. Follow-Up

8.9.1. Safety Follow-Up

The safety follow-up period is the interval between the last dose of study treatment and the scheduled safety follow-up visit, which will occur approximately 30 days after the last dose of itacitinib. Adverse events and SAEs must be reported up until 1) at least 30 days after the last dose of study treatment or 2) until toxicities resolve, return to baseline, or are deemed irreversible, whichever is longer. Reasonable efforts should be made to have the participant return for the 30-day safety follow-up visit and report any AEs that may occur during this period. If the participant cannot return to the site for the 30-day safety follow-up visit (eg, lives far away), the participant should be contacted by telephone for assessment of AEs and SAEs. This contact should be documented in the source and eCRF.

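### Inclusion criterion 4a ends the male sperm-donation ban and contraception at safety follow-up (about Day 56); Appendix A bars donation for 90 days after exposure ends (Day 116 or later)

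*Protocol*

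**What the plan says.** Two places in the protocol set the male restriction.

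- **Section 5.1, criterion 4a.** Men must agree to precautions against fathering children "from screening through safety follow-up and must refrain from donating sperm during this period". The criterion then sends the reader to Appendix A for the permitted methods.
- **Appendix A, male participants.** On donation: "male participants must refrain from donating sperm from screening through 90 days after the end of relevant systemic exposure". On contraception: "Male participants should use a condom from screening through 90 days after the end of systemic exposure", with a recommendation that a partner of childbearing potential also use contraception for 90 days. A vasectomy counts as a highly effective method.

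Three other places fix the dates.

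- **Section 8.8:** "Day 26 is the last expected day of study treatment administration".
- **Section 8.9.1:** the safety follow-up period runs from the last dose to "the scheduled safety follow-up visit, which will occur approximately 30 days after the last dose of itacitinib".
- **Table 3 (Schedule of Activities):** the column for that visit reads "D56 30 d After Last Dose (± 3 d", that is, Day 56 with a window of 3 days either side.

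Section 7.1.2 adds, for those who stop treatment early: "Participants must be followed for safety until the time of the 30-day follow-up visit or until itacitinib-related toxicities resolve" (or return to baseline, or are judged irreversible), whichever is longest.

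**The concern.** Both sperm-donation rules are mandatory and both start at screening, but they stop at different times. Criterion 4a stops at a visit about 30 days after the last dose. Appendix A stops 90 days after systemic exposure ends. No text in the protocol says which prevails.

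The contraception strand is softer. Criterion 4a makes it a condition of entry for the shorter period, and Appendix A recommends it for the longer one.

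Criterion 4a records what a man undertakes when he enrols, and Section 5 insists that the criteria be followed as specified. A site that does so obtains agreement only to about Day 56, and may tell the man he is then free of the restriction while Appendix A still forbids donation and advises contraception. The protocol itself treats paternal exposure as a safety matter: Section 9.7 sets reporting duties for a pregnancy confirmed during it. What is at stake is participant and partner safety. The efficacy results are not affected.

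**Working it through.** The check is day arithmetic on the protocol's own scale (Day 0 = cell infusion).

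**Inputs**

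| Quantity | Value | Source |
|---|---|---|
| Last planned dose | Day 26 | Section 8.8 |
| End of 4a restriction | Safety follow-up | Section 5.1 |
| Safety follow-up visit | 30 days after last dose, ± 3 days | Section 8.9.1, Table 3 |
| End of Appendix A restriction | 90 days after exposure ends | Appendix A |

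**1. Reproduce the protocol's figure.** Safety follow-up = 26 + 30 = Day 56. This matches Table 3. The window is 56 − 3 = Day 53 to 56 + 3 = Day 59.

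**2. End date under Appendix A.** If exposure ends on the day of the last dose, 26 + 90 = Day 116. If it ends *w* days later, the limit is Day 116 + *w*. The documents give no half-life from which to calculate *w*, so Day 116 is the earliest date for a man who completes treatment.

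**3. Gap.**

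- Visit on the nominal day: 116 − 56 = 60 days.
- Visit at the late edge of the window: 116 − 59 = 57 days.
- Visit at the early edge: 116 − 53 = 63 days.
- In each case add *w* if exposure outlasts the last dose.

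**4. Early discontinuation.** If the last dose falls on day *L*, the two end points are *L* + 30 and *L* + 90. The difference is still 60 days, so stopping early moves both dates and leaves the gap. The exception is a man followed longer under Section 7.1.2 because of unresolved toxicity, for whom the gap could be read as shorter.

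**5. Does the visit schedule cover the gap?** Day 116 falls between the Day 90 visit (± 1 week, so Day 83 to 97) and the Day 180 visit (± 2 weeks, so Day 166 to 194). No scheduled contact coincides with the end of the longer restriction, so compliance depends on what the man was told beforehand.

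**6. Who is affected.** The donation mismatch applies to all men. The contraception mismatch applies mainly to men without a vasectomy. There is no matching conflict for women, because the female part of Appendix A lists methods without setting its own end date.

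**The case against.** The best case on the other side is that the two texts can both be obeyed. Criterion 4a does not say that donation is allowed after safety follow-up; it sets a minimum undertaking for entry. Appendix A addresses men already in the study and sets a longer period, so a man who follows it satisfies both. Criterion 4a also directs the site to Appendix A, where the male section is one short paragraph and the condom sentence itself carries the 90 days. Finally, the consent form is not among the documents reviewed and may already state the longer period.

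Part of this stands. Neither rule forces a breach of the other, and a site that opens Appendix A will probably see the 90 days. Only the donation strand sets one mandatory rule against another. That any participant would be misinformed is a possibility and has not been shown.

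The rest does not remove the mismatch. Following the longer rule works only if the man is told of it, and criterion 4a states its own, shorter duration, citing the appendix for methods alone. An unseen consent form cannot be assumed to put this right. Sections 7.1.2 and 8.9.1 allow follow-up or adverse event reporting to continue until toxicities settle, but that depends on an event. It would not carry a man without ongoing toxicity to 90 days, and Section 8.9.1 still ties the safety follow-up period to the 30-day visit.

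**Conclusion.** The concern holds. The protocol gives two mandatory end dates for the ban on sperm donation, and a shorter requirement beside a longer recommendation for male contraception, with no rule of precedence. For a man dosed through Day 26 the dates are about Day 56 and Day 116, a gap of about 60 days (57 to 63 over the visit window). This assumes that exposure ends on the day of the last dose; if it ends later, the gap is wider.

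The documents do not show which period is pharmacologically right, only that both cannot stand as the end date. Severity is minor: the point bears on participant and partner safety, with no effect on sample size, power, type I error or any planned analysis.

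**What to change.** Amend criterion 4a so that both contraception and the ban on sperm donation run from screening until 90 days after relevant systemic exposure has ended. That is the more protective of the two periods and is already in Appendix A. If the sponsor's safety team documents that stopping at safety follow-up is sufficient, bring Appendix A into line with criterion 4a instead. In either case, check that the consent template gives the same end point.

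The cost is one sentence in the protocol and a check of the template. No visit, sample size or analysis changes.
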